- An Alternative PROMS by Mail Method + Phone Contact* (postoperative follow-up only): This method is to be done in the event the Subject is either unable or unwilling to be seen in the clinic office and agrees to complete and return the study required PROMs by mail AND attend a follow-up phone contact visit*. Upon completion of both methods of data collection (in the same interval window), an alternative clinic visit will be considered completed. This type of visit allows for the surgeon portion of the AKS and radiographs to be optional. The details associated with administration of PROMs are described in Section 8.2.1 and apply for this method of data collection A sample cover letter, Contact Form, and Phone Script are provided in Exhibit F.

The definition of a *Phone Contact visit is defined as:

A telephone call with the Study Subject (See Time and Events Table 1-1). In order to optimize the accuracy of survivorship data, enable timely capture of AEs and maximize the chance of good long- term follow-up, contact will be made with each Subject at 3 and 4 years post-operatively. These telephone contact visits will occur in between the 2yr and 5yr clinic visits and will ideally occur within the preferred window. No PROMs are to be completed.

Phone Contact visits will take the form of a telephone call where a member of the study team, typically a Research Coordinator, speaks with the study Subject. The topics to be covered and information to be collected during the call will include: confirmation of the Subject's contact information; assessment of whether there has been a revision or any adverse events to the Subject's implanted knee for the study; reminder to the Subject of their next scheduled visit and the importance of their continued study participation. As an alternative approach if in keeping with sites' standard of care, the data collected via a phone contact visit can be collected face to face (in clinic or virtual) or via mail in lieu of being done over the phone.

Note: If a full clinic visit data set is collected at the phone contact intervals (3 & 4 yrs postoperatively), the site will only be compensated for a phone contact type visit.

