9.3 Interval Windows

The pre-operative assessment is to be done between 180 days prior to the procedure up to day -1 (day zero defined as the day of the index procedure for this study); radiographs for this study may be from 180 days prior to day -1 (or longer if the PI determines they are acceptable for surgical planning). The required window intervals are defined as follows for analysis purposes:

Table 9-1: Interval Windows

Required* Follow-up Intervals (days)								
Pre-op**	Day 0	6 Week	6 Months	1 Year	2 Year	3 Year Contact	4 Year Contact	5 Year
-180 to -1d	0 (Defined as the Day of TKA)	1-90	91-303	304-669	670-1033	1034-1398	1399-1763	1764- 2044
Preferred* F	Preferred* Follow-up Intervals (days)							
Pre-op**	Day 0	6 Week	6 Months	1 Year	2 Year	3 Year Contact	4 Year Contact	5 Year
-90 to -1d								

^{*} Although these are the windows for analysis purposes, narrower "preferred" interval windows have also been included in this protocol

Multiple visits within these defined windows for a single subject may occasionally occur. If this occurs, then for both the pre-op interval the visit closest to the date of surgery will be considered the study visit. Individual pre-op data (i.e. radiographs, PROMs, etc.) may be collected at different pre-op visits and each type of data will be considered separately when considering multiple visits. For post-op intervals the later of the visits will be considered the study visit for analysis purposes.

DSJ_2019_05, Rev D (FINAL) 24 August 2022 DePuy Synthes Products, Inc. - Confidential

^{**} Pre-operative radiographs may be in the window -180 to -1 days (or longer if the PI determines they are acceptable for surgical planning)

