9.5 Handling of Missing Data

Only actual data will be analyzed; there will be no imputation of missing data.

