9.8.4.1 Primary Endpoint and Associated Hypotheses

The primary endpoint is the Functional Responder Rate (FRR) at 1 year. A Functional Responder is defined as:

- A subject that shows at least 20% improvement from baseline and at least a 10-point improvement from baseline in at least 2 of the following categories:
 - o KOOS (ADL)
 - o KOOS (Pain)
 - o KOOS (Quality of Life)

Functional Responder rates are expected to be between 91%-94%. The objective performance criteria for study success is 85%.

$$H_0$$
: FRR $\leq 85\%$

$$H_A: FRR > 85\%$$

The primary endpoint will be performed on the first 225 tibia implanted with the ATTUNE Cementless FB tray (primary and revision procedures, CR FB and PS FB combined) and will be analyzed when these patients have passed the 1 year preferred post-op window (395 days). This analysis will be done on the Per Protocol (PP) population. Study success will be determined using the primary TKA (CR FB and PS FB combined) analysis group.

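### Section 9.3 selects post-operative data by whole visit (the later one) rather than by form, so a film, surgeon AKS or KOOS already recorded in the window can drop out

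*Combined protocol and SAP*

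**What the plan says.** Section 9.3 (Interval Windows) foresees the situation: "Multiple visits within these defined windows for a single subject may occasionally occur". It then gives two rules.

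- **Pre-operative.** The visit closest to surgery is used, with a qualification: "Individual pre-op data (i.e. radiographs, PROMs, etc.) may be collected at different pre-op visits and each type of data will be considered separately". That sentence is confined to pre-operative data.
- **Post-operative.** "For post-op intervals the later of the visits will be considered the study visit for analysis purposes". The unit of selection is the visit. There is no form-level rule and no fallback to an earlier visit in the window.

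The required windows are the analysis windows. The 1-year window is days 304-669 and the 2-year window is days 670-1033 (Tables 1-1 and 9-1).

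Section 8.2.4.1 allows an alternative to the in-clinic visit for a subject who "agrees to complete and return the study required PROMs by mail AND attend a follow-up phone contact visit". Of this route it says: "This type of visit allows for the surgeon portion of the AKS and radiographs to be optional".

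Section 9.5 adds: "Only actual data will be analyzed; there will be no imputation of missing data". Section 9.8.4.1 states: "The primary endpoint is the Functional Responder Rate (FRR) at 1 year". That endpoint is built from three KOOS subscales and is tested against 85%.

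**The concern.** The authors recognised that different forms may come from different visits and dealt with it before surgery only. After surgery, visits carrying different sets of forms are also possible. If the later visit simply replaces the earlier one, a valid form completed inside the window is not analysed, and Section 9.5 gives no way to recover it.

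This differs from choosing between two KOOS forms in one window. Here only one form exists, and the rule passes over it because of the date of another visit.

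At stake are the completeness of the radiographic and surgeon-rated AKS summaries and, less often, the number of knees in the responder rate. The sample size has almost no slack for extra losses: 225 x 0.85 = 191.25, against 191 needed.

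**Working it through.** **1. Can a later visit lack a form that an earlier visit in the same window had?**

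- *Radiographs and surgeon AKS: yes, by a documented route.* Both are optional at an alternative visit (Section 8.2.4.1; Table 1-1 legend). Example: clinic visit with films on day 720, alternative visit without films on day 800. Both fall in days 670-1033. The later visit becomes the study visit, so the 2-year film and surgeon AKS are not selected.
- *KOOS: possible, but less direct.* Both kinds of 1-year clinic visit require KOOS, so the later visit must be an unscheduled or incomplete one, or a bare contact. The Table 1-1 legend for event-driven forms lists a phone or mail contact separately from an alternative visit, and those forms appear in the 1-year column. Example: clinic visit with KOOS on day 365, later attendance without KOOS on day 450. The 1-year window is 669 - 304 + 1 = 366 days wide. The primary analysis waits until the 225 knees have passed day 395, by which time the earliest implanted will be further on.

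**2. Does another section restore the earlier form?** I found none. Section 8.2.2 prefers the 6-week film when films exist at both 6 weeks and 6 months, but that chooses between windows, not within one.

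**3. The plan's own figure.** Inputs from Sections 9.4 and 9.7: null 85%, assumed rate 91%, one-sided alpha 0.05, 80% power, normal approximation, 15% attrition.

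n = [z(0.95) x sqrt(0.85 x 0.15) + z(0.80) x sqrt(0.91 x 0.09)]^2 / (0.91 - 0.85)^2
= [1.6449 x 0.35707 + 0.8416 x 0.28618]^2 / 0.0036
= 190.5, so 191.

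191 / 0.85 = 224.7, so 225. Both figures reproduce, and selecting by form would not change them.

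**4. Power if knees are lost.** The documents give no rate, so I assume that 1-3% of the 191 knees lose their KOOS in this way, beyond the 15% allowance.

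Power = Phi{[sqrt(n) x 0.06 - 1.6449 x 0.35707] / 0.28618}

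| Share lost | n | Power at 91% |
|---|---|---|
| 0 | 191 | 80.1% |
| 1% | 189 | 79.7% |
| 2% | 187 | 79.2% |
| 3% | 185 | 78.8% |

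**5. False success if the lost knees respond less often.** Assume a true rate of 85% overall and 75% in the affected knees; both are illustrations. The expected rate among the remaining knees is (0.85 - f x 0.75)/(1 - f), where f is the share lost. False success is the exact binomial chance that the z-test rejects, averaged over n within 6 of 191(1 - f) to smooth out discreteness.

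| Share lost | Expected rate | False success |
|---|---|---|
| 0 | 85.0% | about 4.7% |
| 1% | 0.8425/0.99 = 85.1% | about 4.9% |
| 2% | 0.8350/0.98 = 85.2% | about 5.4% |
| 3% | 0.8275/0.97 = 85.3% | about 5.9% |

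**The case against.** **The text never says that earlier forms are discarded.** Section 9.5 speaks of analysing actual data, and Section 9.8.4.2 bases its remaining secondary summaries on all data from per-protocol subjects. A programmer could therefore apply the later-visit rule form by form. This stands as a reason to call the loss a literal consequence rather than a demonstrated one. It does not settle which reading is meant, since the form-by-form sentence in 9.3 is limited to pre-operative data.

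**A reader might infer that a mailed KOOS followed by the phone call makes the KOOS missing.** The documents do not support that. Section 8.2.4.1 treats the two parts, once both are done in the same window, as one completed alternative visit. That visit contains a KOOS, so the multiple-visit rule does not apply.

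**The KOOS case needs a visit outside the two defined kinds of clinic visit.** This is correct and makes the case rarer. A later contact in the window is still possible, and 9.3 does not say that only complete visits count.

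**The film case is unusual.** The alternative route is meant for subjects who cannot or will not attend, so its use after a clinic visit in the same window would be uncommon. It is nevertheless permitted.

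**The attrition allowance may already cover such losses.** Section 9.7 does not say what attrition includes. If it includes these knees, planned power does not change. Moreover, exact power of the z-test rule moves up and down with n (80.2% at 191, 81.5% at 189, 82.7% at 187, 77.3% at 185), so small losses show no steady decline.

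**Conclusion.** The gap is real on the plain text: selection is by form before surgery and by whole visit after it, with no fallback. It is best documented for radiographs and the surgeon AKS, and possible but less direct for the 1-year KOOS.

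The effect on the primary result is probably small. Under the assumed 1-3% loss, power falls by 0.4 to 1.3 percentage points. With a 75% response rate in the affected knees, false success rises by about 0.2 to 1.2 points. Neither the frequency nor the response rate comes from the documents.

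A reader might infer that the rule inflates the responder rate, because knees with problems attract extra visits. That is plausible but not shown: the plan gives no data linking extra visits to poor outcome, and subjects whose femoral or tibial component is revised are withdrawn in any case (Section 8.6). A reader might also infer a large loss of power or a badly inflated error rate. That would need affected shares well above what a plan describing multiple visits as occasional can support.

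**What to change.** In Section 9.3, state that for post-operative intervals each type of data (KOOS, AKS patient section, AKS surgeon section, FJS-12, EQ-5D-5L, radiographs) is considered separately, and that the later-visit rule applies only among visits in the window at which that form was completed. Settle this before the primary analysis, because it bears on the study's only hypothesis test.

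The cost is one or two sentences and a small programming change. It needs no new data and no change in sample size. The downside is that forms within one interval may carry different dates, which the plan already accepts before surgery. The rule for when an alternative visit counts as complete (Section 8.2.4.1) is a separate matter and need not change.

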9.4 Levels of Significance

Where estimated, all confidence intervals will be 95% confidence intervals. For the primary endpoint hypothesis test an alpha = 0.05 will be used to determine statistical significance. No adjustments will be made for multiplicity as this is the only hypothesis in the study.

9.5 Handling of Missing Data

Only actual data will be analyzed; there will be no imputation of missing data.

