3.2 Study Design Rationale

The study is designed as a non-comparative, multi-center study with each site initially having a cohort of approximately 30 Subjects to recruit (maximum of 50 per site). The follow-up period of 5 years was selected to assess the early period (the first year) when any initial problems may become evident with initial fixation and stability associated with cementless fixation, as well as the medium-term period (out to five years) which is a good indicator of longer-term survivorship. Longer-term survivorship will become available as the product is captured in National Joint Registries in various markets in the absence of any other studies being planned at this point in time.

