8.4 Discontinuation of Subject Participation

Study participation may be discontinued through screen failure, not receiving the tibial base implant, revision of the femoral and/or tibial component(s), withdrawal of consent, or death. Table 8-8 describes how data will be captured on Subjects that are discontinued prior to receiving the study device while Table 8-9 describes post-op withdrawal scenarios. In all cases, once a subject is enrolled (per Figure 8-1), if they discontinue study participation, the Subject Completion/Discontinuation eCRF must then be completed.

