8.5 Post-operative Withdrawal of Enrolled Subjects

A post-operative withdrawal is a Subject who has signed the Informed Consent Document (ICD), has been implanted with a study device, and is later withdrawn from study participation (i.e., withdrawal of consent, revision of any study TKA component, death, etc.). Table 8-9 describes post-operative withdrawal scenarios and the eCRF to be completed. Further description of revision is provided in Section 8.6 Revisions. No data after the date of withdrawal will be included in the clinical analysis.

Table 8-9: Post-operative Withdrawal Scenarios

Example	Action	Follow Up
Subject withdraws consent	 Study site documents Subjects' request for withdrawal from study. Complete Study Completion/Discontinuation eCRF 	Do not continue
Surgeon preference / medical opinion	 Study site documents Surgeons' reason for patient withdrawal from study (should occur under very limited conditions, in order to avoid investigator bias). Complete Study Completion/Discontinuation eCRF 	Do not continue
Death	Complete Adverse Event eCRF Complete Study Completion/Discontinuation eCRF	Do not continue
Revision	See Section 8.6 and Table 8-10 Revision Examples	

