8.6 Revisions

A "revision" is defined as a surgical procedure of the affected knee where one or more of the TKA components (metal femoral component and/or metal tibial base, polyethylene insert, or patella polyethylene resurfacing component) are removed. Should it be necessary for the Subject to undergo a revision of any ATTUNE Cementless Femoral and/or Tibial Base component between the time of enrolment and completion of the study data acquisition, the Subject is to be withdrawn from study participation. Thus, both an Adverse Event (AE) eCRF and the Subject Completion/Discontinuation eCRF must be completed (see Table 8-9). Note that if a tibial insert is exchanged and/or a resurfaced patella is revised, but both the femoral and tibial base components remain, then an AE eCRF must be completed, but the subject is not to be withdrawn from the study.

A "re-operation" is defined as any surgical procedure of the affected knee in which none of the TKA components are removed. Examples include irrigation & debridement without tibial insert exchange or the resurfacing of a previously unresurfaced patella. These subjects are not to be withdrawn. An Adverse Event (AE) eCRF must be completed.

Table 8-10: Revision and Reoperation Examples

Example	Actions	Follow Up
Removal / revision of metal Tibial Base and/or Femoral component	 Complete Adverse Event eCRF Complete Revision/Reoperation eCRF Complete Study Completion/Discontinuation eCRF 	Do not continue
Tibial Insert polyethylene exchange	Complete Adverse Event eCRF Complete Revision/Reoperation eCRF	Continue
Revision of a previously resurfaced patella	 Complete Adverse Event eCRF Complete Revision/Reoperation eCRF 	Continue
Resurfacing of a previously unresurfaced patella in combination with a Tibial polyethylene exchange	 Complete Adverse Event eCRF Complete Revision/Reoperation eCRF 	Continue

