9.7 Sample Size Justification

The primary endpoint in this study will be to estimate the Functional Responder (defined below in Section 9.8.4.1) rate at 1 year and demonstrate superiority to the 85% objective performance criteria. Functional Responder rates are anticipated to be between 91-94% in primary TKA based on a previous study of ATTUNE Cemented and ATTUNE Cementless CR RP knees. Using the lowest anticipated rate of 91%, a sample size of 191 knees will provide at least 80% power to show superiority of the Functional Responder rate compared to the objective performance criteria of 85%, with 95% confidence using a one-sided, normal approximation, one-proportion test and associated confidence interval. Accounting for up to 15%

DSJ_2019_05, Rev D (FINAL) 24 August 2022 DePuy Synthes Products, Inc. - Confidential

attrition at 1 year, the sample size population for analysis of the primary endpoint was increased to the first N=225 knees enrolled.

Due to various global requirements and anticipated regulatory submissions the sample size is increased to N=300 per configuration.

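### As the rules most naturally read, a primary TKA knee whose tibial base or femoral component is removed before its 1-year KOOS drops out of the primary denominator; the plan should state this and say whether the 85% OPC was set the same way

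*Combined protocol and SAP*

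**What the plan says.** Section 9.8.4.1 defines a responder through KOOS alone: "A subject that shows at least 20% improvement from baseline and at least a 10-point improvement from baseline", in two or more of the ADL, Pain and Quality of Life subscales. The analysis uses the Per Protocol (PP) set, and success is judged in the primary TKA group.

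Four other rules bear on a knee that loses its tibial base or femoral component early:

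- **Withdrawal.** Section 8.6 says that after such a revision "the Subject is to be withdrawn from study participation". Section 8.4 and Table 8-10 agree.
- **Later data.** Section 8.5: "No data after the date of withdrawal will be included in the clinical analysis".
- **Missing data.** Section 9.5: "Only actual data will be analyzed; there will be no imputation of missing data".
- **Sample size.** Section 9.7 needs 191 knees. To allow for up to 15% "attrition at 1 year, the sample size population for analysis of the primary endpoint was increased to the first N=225 knees enrolled".

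The PP set (9.6.3) requires one post-operative evaluation in the 6-week or a later window. It does not require a 1-year KOOS. Revisions are analysed by Kaplan-Meier, and adverse events are tabulated, both on the Safety set (9.6, 9.8.4.2).

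**The concern.** No section gives a responder status to a knee removed before its 1-year KOOS. The rules above most naturally take it out of the denominator, because it has no 1-year score, none may be imputed, and 9.7 treats knees without 1-year data as lost to the analysis.

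These knees are not missing at random. Section 3.2 justifies the follow-up partly by "the early period (the first year) when any initial problems may become evident with initial fixation and stability associated with cementless fixation", and early removal of a fixed component is the clearest form of such a problem. On the natural reading, these failures do not count against the device in the only hypothesis test of the study, whose data are intended for CE mark registration (3.1).

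The benchmark has the same gap. Section 9.7 says "Functional Responder rates are anticipated to be between 91-94% in primary TKA based on a previous study", but not whether that range, or the 85% OPC, counts revised knees as failures. A reader cannot tell whether the comparison is like for like.

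Two groups are outside the point: insert-only or patella-only revisions, which 8.6 and Table 8-10 keep in follow-up, and knees revised after a 1-year KOOS has been recorded (that window opens on day 304).

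**Working it through.** **Inputs.** From 9.4, 9.7 and 9.8.4.1: null rate 0.85, anticipated rate 0.91, one-sided alpha 0.05, normal-approximation one-proportion test, power 80%, n = 191, attrition 15%, N = 225. The documents give no revision rate, so every r below is an assumption. I also assume that all 191 evaluable knees are primary TKA. Table 6-1 supports this, but 9.8.4.1 lets the first 225 include revision procedures.

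**1. The plan's own figures.** n = [(1.645·√(0.85·0.15) + 0.842·√(0.91·0.09)) / 0.06]² = 190.5, rounded up to 191. Then 191/0.85 = 224.7, rounded up to 225. Both reproduce. At n = 191 the test passes with 171 or more responders; exact size is 0.0445 and exact power at 91% is 0.802.

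**2. The factor.** Let R be responders, E evaluable knees and k knees removed before their 1-year KOOS. The observed-KOOS rate is R/E. The rate counting removals as failures (the composite) is R/(E+k). Their ratio is (E+k)/E = 1/(1-r), with r = k/(E+k). So r is a share of evaluable plus removed knees, not of all 225.

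**3. Chance of success if the composite is truly 85%.** The observed-KOOS rate is then 0.85/(1-r), and the chance of success is P(X ≥ 171) with n = 191. The implied number of removals is 191·r/(1-r).

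| Assumed r | Removals beside 191 evaluable | Observed-KOOS rate | Chance of success |
|---|---|---|---|
| 0 | 0 | 0.8500 | 4.45% |
| 0.25% | 0.5 | 0.8521 | 5.3% |
| 0.5% | 1.0 | 0.8543 | 6.2% |
| 1% | 1.9 | 0.8586 | 8.4% |
| 2% | 3.9 | 0.8673 | 15.0% |

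**4. The planned result.** 0.91 × 191 = 173.8, about 174 responders. With z = (x/n − 0.85)/√(0.85·0.15/n) and critical value 1.645:

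- no removals, 174/191: z = 2.361, passes
- four removals counted as failures, 174/195: z = 1.655, passes
- five removals, 174/196: z = 1.480, fails (5/196 = 2.6%)

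**5. The opposite mismatch.** If the OPC was set on observed KOOS, and the observed-KOOS rate is truly 85%, the composite is 0.85(1-r). Testing it at n = 191 passes 3.8%, 3.2%, 2.2% and 1.0% of the time at the same four values of r. That is stricter on the device than the planned 4.45%.

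**6. Power if the composite decides and the 91% excludes revisions.** The rate becomes 0.91(1-r), and removed knees are added back to n.

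- r = 1%: rate 0.9009, n = 193, pass at 173 or more, exact power 0.640
- r = 2%: rate 0.8918, n = 195, pass at 174 or more, exact power 0.549

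Both compare with 0.802 as planned. Exact power moves in steps with the integer critical value, so these figures are illustrations.

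**The case against.** The strongest reply is that the plan has chosen its rate. The objectives tie the 85% to the KOOS questionnaire, 9.8.4.1 uses only KOOS change, 9.5 limits analysis to observed data, and 9.7 sizes the study on knees left after attrition. On that view the observed-KOOS rate is the estimand, the test is valid for it, and revision is reported separately by Kaplan-Meier, including at 1 year. Separating function from survivorship is a legitimate design, and 3.3 gives a functional rationale for the primary endpoint.

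Most of this stands. The text does point to the observed-KOOS rate, and removals are not hidden. What it does not answer is that neither survivorship nor adverse events enter the success rule, and that the basis of the OPC is unstated.

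A second literal reading also exists. A removed knee with one post-operative evaluation stays in the PP set under 9.6.3. Since it shows no improvement at 1 year, it could be scored as a non-responder. That fits poorly with 9.5 and with the step from 225 to 191, but two analysts could defend different denominators.

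A reader might go further and infer that the planned test has an inflated type I error of up to 15%. The documents do not support that. Those figures need both an assumed r and an OPC that counts removals as failures, and no section says the OPC does.

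**Conclusion.** The point holds in a limited form. Following the plan most naturally takes primary TKA knees with early tibial base or femoral component removal out of the only success test, and the plan does not say so. The responder rate then applies to unrevised knees with a 1-year KOOS and is higher than the composite by 1/(1-r).

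The expected size is small: close to nil at r of 0.25%, and five removals beside 191 evaluable knees are needed to reverse the planned result. It matters mainly for a result near the threshold. I am confident about the silence in the text; the numerical effect rests on assumed values of r, on all evaluable knees being primary TKA, and on an OPC basis that the documents do not give. It should be fixed before the readout because the denominator otherwise depends on who programs it.

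**What to change.** 1. **Section 9.7:** state whether the 85% OPC and the 91% each count revisions as failures. This comes first, because it determines which rate should be tested.
2. **Sections 9.5 and 9.8.4.1:** state the denominator. Pre-specify an analysis that keeps in every primary TKA knee among the first 225 with tibial base or femoral component removal before its 1-year KOOS and counts it as a non-responder. Report it beside the observed-KOOS rate, and name in advance which one decides success, matching the basis of the OPC. If the composite decides and the 91% excludes revisions, restate the power with removed knees added back to n.
3. **Other missing 1-year KOOS:** keep the observed-case analysis and add a pre-specified tipping-point sensitivity analysis.
4. **Sections 8.5, 8.6 and Table 8-10:** reconcile the wording. Section 8.5 gives revision of any study component as an example of withdrawal, while 8.6 and the table limit withdrawal to the femoral component and tibial base. Section 8.5 refers on to 8.6, so this looks like loose wording.

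The cost is a few sentences and a little programming. Table 8-10 already requires removals to be recorded on the adverse event, revision/reoperation and completion/discontinuation forms. No extra data collection or later readout is needed. The downside is a slightly lower figure beside the observed-KOOS rate and, if the composite decides, a lower stated power: about 64% at r of 1% and 55% at 2% if the 91% excludes revisions.
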